Volatile compounds such as acrolein and crotonaldehyde may also contribute to lung cancer induction in smokers. Acrolein is a highly toxic agent in cigarette smoke, causing cilia-toxicity among other effects in the lung. One study has shown that acrolein causes a pattern of DNA damage in the p53 tumor suppressor gene similar to that observed in lung tumors of smokers. We have demonstrated the presence of substantial quantities of acrolein-DNA adducts in human lung DNA. Crotonaldehyde, a structural homologue of acrolein, also forms DNA adducts in the human lung, and these are known to be mutagenic, although crotonaldehyde has not been shown to be carcinogenic to the lung. Acrolein and crotonaldehyde are detoxified by reactions with glutathione, and the resulting conjugates are excreted in the urine as 3-hydroxypropylmercapturic acid (3-HPMA) and 3-hydroxy-1-methylpropylmercapturic acid (HMPMA), respectively. These mercapturic acids can be readily measured by established and analytically validated methods, and are related to cigarette smoking. Previous research shows levels of these mercapturic acids were unusually elevated in Native Hawaiians, an aspect that will be further investigated in Project 4.

Cadmium (Cd) is a human lung carcinogen, with cigarette smoking being one of the major sources of exposure. Urinary Cd increases with age and smoking, as major determinants of its levels. A statistically significant association between urinary Cd levels and lung cancer mortality in men from the NHANES III cohort has been reported. While there is some overlap in urinary levels of Cd between smokers and non-smokers, the levels of this biomarker have been demonstrated to increase with smoking. Exposure to Cd has been shown to cause hypermethylation of tumor suppressor genes and was inversely associated with LINE1 methylation, which is a common epigenetic event in carcinogenesis.

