**Aim 1:** Evaluation of ethnic differences in DNA adducts in oral cells quantified in 100 smokers from Core B in each of three ethnic groups. This aim will quantify DNA adducts of acrolein, crotonaldehyde, NNN, NNK, and formaldehyde and identify ethnic differences in levels of these adducts. After QC, outlier identification, analysis of duplicate samples for laboratory variation and batch effects we will fit linear regression models to the (possibly log or power-transformed) adduct levels to allow for differences by age, sex, BMI, TNE and CPD while examining ethnic group differences. The SAS procedure GLM will be used to provide adjusted means (LS means) and to test for the significance of the observed ethnic differences in those means.

As in Project 3, Aim 1, for a given outcome (DNA adduct) we will have 80 percent power to detect a difference between any two ethnic groups which amounts to approximately 6 percent of the total variance of a given outcome. We can also examine the joint effects of smoking and ethnicity in the total of 300 Core B participants and will have 80 percent power to detect ethnicity x smoking interactions that explain at least an additional 1 percent of variation for any outcome.

**Aim 2:** There are two sub aims to Aim 2. The first is to compare urinary metabolites in both smokers and nonsmokers in the three ethnic groups. The main hypothesis is that acrolein and crotonaldehyde metabolites, as well as metabolites from oxidative damage and

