inflammation are higher in Native Hawaiian non-smokers than in the other 3 ethnic groups, and that this is the reason that acrolein and crotonaldehyde metabolites were higher in Native Hawaiian smokers than Japanese American smokers in our published study. We will also compare the levels of the urinary metabolites in the smokers from the three ethnic groups. We will also compare smokers to non-smokers from each ethnic group (for metabolites of acrolein, and crotonaldehyde and biomarkers of oxidative damage and inflammation). Sub aim 2 is to relate DNA adducts measured for the 300 participants in Core B to urinary metabolites of TNE, total NNAL, mercapturic acids of acrolein, and crotonaldehyde measured in the same individuals. After QC, examinations of batch effects and laboratory variation, outlier detection, transformation to normality, we will estimate the ethnic differences and provide linear regression estimates of the relationships between the DNA adducts and metabolites. For sub aim 1 we will compare the urinary metabolite levels in each group of 100 with the other groups. We will use a p-value for any pairwise comparison of 0.003 as protection against type I error. For sub aim 2 since we anticipate that many different analyses will be performed (each DNA adduct against each relevant metabolite) we will use a Bonferroni-corrected p-value of  $0.05/50 = 0.001$  to declare significance in these analyses. Detectable effects will correspond to approximately 3 percent of variance of the DNA adducts explained.

**Aim 3:** Identification and quantification of known and previously unknown DNA adducts. This aim has two sub-aims. The first is to identify known and unknown DNA adducts related to smoking status among 50 current smokers and never smokers of single ethnic group (Whites). The second sub aim is to determine ethnic differences in DNA adduct levels found to be elevated in smokers in the first sub-aim. DNA oral cell adducts will be measured in smokers from Core B. Because of cost and time considerations 20 smokers with high levels of the (acrolein and crotonaldehyde) adducts measured in Project 4 Aim 1 will be selected for analysis of sub aim 2.

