**Statistical Analysis and Power.** For sub aim 1 we will test for differences in DNA adduct levels between smokers and never smokers using parametric or (if appropriate) non-parametric single degree of freedom tests (t-test, Wilcoxon, etc.) Because it is anticipated that several hundred adducts (known + unknown) will be measured we will use a Bonferroni criteria of  $.05/200 = 0.00025$  in order to declare that the observed differences are statistically significant. With 50 participants per group we will be able to detect (with 80 percent power) a smoking difference explaining 18 percent of variation of the adduct level, equivalent to about 1 standard deviation of the within group (smokers, never-smokers) variation of a given DNA adduct.

For sub aim 2 we analyze 20 participants per group and test for ethnic differences in adduct levels for the adducts shown to be elevated in smokers. Our main comparison is between the high risk group (native Hawaiians) and the other groups (Japanese and Whites). Assuming that 50 of the adducts are elevated in smokers we will use a p value of  $0.05/50=.001$  in our hypothesis testing as protection against multiple comparisons. For a given adduct we will be able to detect a difference of about 1.2 standard deviations amounting to 25 percent of variability explained by ethnicity (Native Hawaiian vs Japanese American + White).

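### Does choosing high-adduct smokers by an undefined rule undermine the ethnic comparison in Project 4, Aim 3, sub aim 2?

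*Combined protocol and SAP*

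**What the plan says.** Section 16, Project 4, Aim 3 has two sub aims. The first screens known and unknown adducts in White smokers and never smokers. The purpose of the second is given as "The second sub aim is to determine ethnic differences in DNA adduct levels found to be elevated in smokers in the first sub-aim". The plan limits the number of samples for a practical reason, "Because of cost and time considerations", and chooses them as follows: "20 smokers with high levels of the (acrolein and crotonaldehyde) adducts measured in Project 4 Aim 1 will be selected for analysis".

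The paragraph on analysis and power gives the size by group: "For sub aim 2 we analyze 20 participants per group and test for ethnic differences in adduct levels". The main contrast is Native Hawaiians against Japanese Americans and Whites together, at a p-value of 0.001, and the plan states that "we will be able to detect a difference of about 1.2 standard deviations amounting to 25 percent of variability explained by ethnicity".

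The selecting adducts come from Aim 1, which is described as "Evaluation of ethnic differences in DNA adducts in oral cells quantified in 100 smokers from Core B in each of three ethnic groups".

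**The concern.** Smokers are chosen because two adducts are high, and adduct levels are then compared between ethnic groups in those smokers. The plan gives no threshold or rank for high, no way of combining the two adducts, and no statement that ranking is done separately by ethnic group. The stated purpose is not limited to smokers with high adducts, and the power figure makes no allowance for selection.

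The selecting adducts may themselves differ by ethnicity. Section 2 says that "levels of these mercapturic acids were unusually elevated in Native Hawaiians", and Project 4, Aim 2 says that "acrolein and crotonaldehyde metabolites were higher in Native Hawaiian smokers than Japanese American smokers in our published study". If one cut-off served all groups, the Native Hawaiians selected would stand less far above their own mean than the others do above theirs. The contrast in any correlated adduct would then shrink. At stake would be a diluted main comparison, or a result taken to describe all smokers when it comes from the upper end of the distribution.

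**Working it through.** **1. The plan's own figure.** Inputs from Section 16, Project 4, Aim 3: 20 Native Hawaiians against 20 + 20 = 40 others, alpha 0.001. Two-sided testing is assumed, and so is 80% power, which the plan states for sub aim 1 only.

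- Noncentrality at 1.2 SD: 1.2 × √(20 × 40 / 60) = 4.38. The critical t on 58 df is 3.47, so power is 81.2%. At 1.19 SD it is 80.3%.
- Variance explained: with p(1 − p) = (1/3)(2/3) = 0.222, 1.44 × 0.222 / (1 + 1.44 × 0.222) = 24.2%.

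The stated 1.2 SD and 25% are therefore correct for unselected smokers.

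**2. Ranking within each ethnic group.** Take the top 20 of 100 in each group, with equal spread (SD 1) and correlation r between the selecting and the tested adduct. The documents give no r; 0.3, 0.5 and 0.7 are assumed. At r = 0 selection has no effect.

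- The top 20 of 100 lie on average 1.39 SD above their group mean on the selecting adduct, and its variance among them is 0.222 (simulated order statistics).
- Every group's mean on the tested adduct therefore rises by the same 1.39r, that is by about 0.4, 0.7 and 1.0 SD. The rise cancels in the difference, which stays at 1.20 SD.
- The SD of the tested adduct falls to √(1 − r²(1 − 0.222)) = 0.964, 0.897 and 0.787. The standardised difference becomes 1.2 divided by that SD: 1.24, 1.34 and 1.53. Power is 85%, 91% and 98%.

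The contrast still estimates the difference among all smokers, and the plan's power figure is conservative.

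**3. One cut-off for all groups, then 20 per group.** Assume the selecting adducts are 0.5 SD higher in Native Hawaiians than in both other groups. That matches the 6% of variance Aim 1 is sized to detect: 2 × √(0.06 / 0.94) = 0.505 SD.

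- At the pooled median, selected Native Hawaiians lie 0.598 SD above their own mean and the others 0.906 SD above theirs. The 1.2 SD contrast becomes 1.2 − r(0.906 − 0.598) = 1.11, 1.05 and 0.98 SD.
- At the pooled top third the values are 0.868 and 1.221, giving 1.2 − r × 0.353 = 1.09, 1.02 and 0.95 SD.
- Power is between 74% and 80% across these six cases.
- If the excess is over Japanese Americans only, simulation (10,000 runs per case) gives 1.08–1.15 SD and 79–91% power.
- A selecting adduct re-tested after a common cut-off would show a true 0.5 SD difference as 0.19 SD (median) or 0.15 SD (top third).

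**4. Unequal spread.** Assume the Native Hawaiian spread is 1.25 times larger in both adducts, r = 0.5, and equal group means.

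- Within-group ranking produces a spurious 0.5 × 1.39 × 0.25 = 0.17 SD.
- A simulation of 20,000 runs per rule gives rejection at the nominal 0.1% level in about 0.7% of runs for within-group ranking. A pooled-median cut-off gives about 0.3% with a shift of 0.10 SD, and random sampling about 0.2%.

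**The case for a change.** The strongest argument for a change is that the rule should be written down before Aim 1 results are used to choose samples, at the cost of a few sentences and no extra assays. Aim 1 protects only the adducts it measures. The other known and the previously unknown adducts are seen only in the selected smokers. Equal spread, which makes within-group selection harmless for the contrast, is not stated in the plan. All of this stands as far as it goes: a reader cannot reconstruct the rule from the text, and absolute adduct levels from this sample would not describe smokers in general.

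It does not show that the planned comparison is wrong. The sub aim concerns differences, not absolute levels, and the plan says openly that the smokers are selected. The shrinkage needs three things together: a common cut-off, a material correlation, and an excess of oral-cell adducts in Native Hawaiians. The evidence for the last is urinary and comes without a size, and the comparison named under Aim 2 is with Japanese Americans only. A much larger loss (0.62–1.00 SD, 26–61% power) appears only if the selecting adducts are 1.2 SD higher than in both groups, which the documents do not suggest.

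The obvious remedies are not clear gains either. Fixing a top-fifth rule would tie the plan to the option most sensitive to unequal spread. Random sampling would give power of about 81% instead of 85–98% and risks samples below detection.

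**Conclusion.** No change to the plan is needed. The undefined selection rule is missing detail that analysts can fill sensibly: the analysis paragraph already fixes 20 per group, which points to selection within each ethnic group and also settles the looser mention of 20 smokers. Under that reading, with equal spread, the contrast stays at 1.20 SD and power is 85–98%, against 81% for unselected smokers. Under the less natural common cut-off, at the effect size Aim 1 is sized for, the contrast is about 0.95–1.11 SD and power 74–80%, a modest loss in one exploratory sub aim.

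Choosing high-adduct smokers to limit assay cost is a fair and disclosed trade-off, and the ethnic comparison of the selecting adducts rests on Aim 1 in all 100 smokers per group. The conclusion depends on assumed correlations of 0.3 to 0.7, normality and roughly equal spread, none of which the documents give. If spread differed between groups, the result might not carry over to all smokers; that is a matter for interpretation when the sub aim is reported.

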## 17 Data and Biospecimen Sharing Plan

The institutions involved in this project are committed to the sharing of research data and samples, consistent with the regulations and policies of the NIH. The investigators involved in this project intend to share findings from its research through publications and presentations. Institutions and individuals wishing to access any resources or data must contact the Principal Investigator ([name]). Data will be available in two formats. One

will be a summary of the data, with graphs and tables, posted as pdf files. Also, data will be available as raw individual-level data for analysis. However, this will not be available until papers are accepted for publication. Data generated by this grant will be made to outside investigators, according to NIH Guidance. Persons requesting data must do so in writing, identifying the affiliation and how the data will be used. When data are shared, there will be no limits placed on how the data will be used, and co-authorship is not required as a condition for receiving data. Users will agree, however, that the recipient must not transfer the data to other users and that the data are only to be used for research purposes. The PI will require requestors of data to sign a data and biospecimen sharing agreement that will ensure (1) Use of the data and/or samples only for research purposes unless otherwise agreed and not to identify any individual or personal information (2) Data security using appropriate technology/firewalls, (3) Destruction or return of data after data analysis and (4) Proper citation in publications or other written materials. A record of transfer of data and a copy of the dataset that was distributed will be kept by University of Minnesota.

## **18 Conduct of the Study**

### **18.1 Good Clinical Practice**

The study will be conducted in accordance with the appropriate regulatory requirement(s). Essential clinical documents will be maintained to demonstrate the validity of the study and the integrity of the data collected. Master files will be established at the beginning of the study, maintained for the duration of the study and retained according to the appropriate regulations.

### **18.2 Ethical Considerations**

The study will be conducted in accordance with ethical principles founded in the Declaration of Helsinki. The UMN and UH IRBs will review all appropriate study documentation in order to safeguard the rights, safety and well-being of the patients. The protocol, consent, written information given to the patients, safety updates, annual progress reports, and any revisions to these documents will be provided to the IRBs for review by the investigators.

### **18.3 Informed Consent**

All potential study participants will be given a copy of the IRB-approved consent to review. The investigator or designee will explain all aspects of the study in lay language and answer all questions regarding the study. If the participant decides to participate in the study, he/she will be asked to sign and date the consent document. Patients who refuse to participate or who withdraw from the study will be treated without prejudice.

2.	Smokes 5 cigarettes per day in the past three months;		
3.	≥ 21 years of age		
4.	Consumes 14 or fewer drinks of alcohol per week;		
5.	Generally good health (determined by review of medical history)		
6.	Able to provide written voluntary consent before performance of any study related procedure.		

## Eligibility Checklist – page 2 of 2

### **EXCLUSION CRITERION**

**A “YES” response to the following disqualifies the participant from study entry.**

		Yes	No
7.	Current use of other nicotine containing products for > 4 times per month (and no use of any nicotine-containing products except cigarettes for 2 weeks prior to their study visits);		
8.	Acute or uncontrolled medical or psychiatric conditions;		
9.	Currently taking any medications that affect relevant metabolic enzymes or anti-inflammatory medications such as ibuprofen (this will be reviewed by study investigators on a case-by-case basis);		
10.	Active infection (e.g., influenza, cold, respiratory infection, sinus infection) at the time of the visit;		
11.	Pregnant or nursing or planning on becoming pregnant during the study;.		
12.	Unable to read and understand English.		

Date consent form signed by participant and research staff: \_\_\_\_\_

Having obtained consent and reviewed each of the inclusion/exclusion criteria, I verify that this participant is:

Eligible  Ineligible Date registered \_\_\_\_\_

\_\_\_\_\_  
Signature of person verifying eligibility

\_\_\_\_\_  
Date
